4.1.2 Per Protocol (PP) Population

The per protocol population will include all patients randomized in Group A and Group B, who received at least one dose of study medication if in Group A, and who had none of the major protocol violations or deviations listed below. Patients will be assigned to the treatment group as per actual treatment they received.

The criteria for exclusion from the PP populations are defined as:

1. those in Group A who meet any of the criteria below, including:
 - received less than 39 doses of PEG-IFN or took $\leq 80\%$ of treatment duration of PEG-IFN (i.e., less than 39 weeks of PEG-IFN treatment)
2. those in Group A and Group B who meet the criteria below:
 - HBeAg negative at screening
3. those in Group A and Group B who meet the criteria below:
 - ALT $\leq 1xULN$ or ALT $> 10xULN$ at both screening and baseline
4. those in Group A and Group B who meet the criteria below:
 - Who have had any of the treatment within 6 months prior to baseline or during study (Group A: up to 24 weeks after the end of treatment; Group B up to 24 weeks after the end of principle observation period or prior to switch if switch occurs) as: interferons, lamivudine, tenofovir, emtricitabine, adefovir, entecavir, telbivudine
5. those in Group A and Group B who meet the criteria below:
 - Neutrophil count $< 1.5 \times 10^9$ cells/L at screening

6. those in Group A and Group B who meet the criteria below:

- Platelet count < 90×10^9 cells/L at screening

7. those in Group A and Group B who meet the criteria below:

- Hemoglobin < lower limit of normal (LLN) at screening

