2.3 DETERMINATION OF SAMPLE SIZE

Sample size is based on the χ^2 test statistic. Assuming a 32% HBeAg seroconversion rate for Group A (PEG-IFN) and 10% for Group B (untreated control), a total sample size of 145 patients provides at least 80% power at the 0.05 level of significance with a two-sided χ^2 test². The sample size shall be increased by 10% and rounded to 160 patients to allow for advanced fibrotics (Group C).

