3. STUDY CONDUCT

3.1 RANDOMIZATION ISSUES

After signing informed consent/assent and meeting screening parameters, patients without advanced fibrosis or cirrhosis (assessed by liver biopsy performed within 2 years prior to baseline) will be randomized 2:1 into the PEG-IFN treatment (Group A) or untreated control (Group B) respectively. Stratification will be performed by genotype (A versus non-A) and ALT (<5xULN versus ≥5xULN). Patients with advanced fibrosis (assessed by liver biopsy performed within 9 months prior to baseline) will be assigned to PEG-IFN treatment (Group C). Patients in Group A and Group C will receive PEG-IFN for 48 weeks. Group and dose, if applicable, will be assigned by an interactive voice or web response system (IxRS).

The randomization list for the study was created by the IxRS vendor using their internal validated process. The study statistician reviewed a dummy randomization list that was created using the same validated process.

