4.4.1 Primary Efficacy Endpoint

4.4.1.1 Definition of Primary Efficacy Endpoint

The primary efficacy endpoint is HBeAg seroconversion at 24 weeks after the end of treatment/ principal observation period for Group A and Group B. HBeAg seroconversion

is defined as absence of HBeAg (that is, a negative result for HBeAg) and presence of anti-HBe (that is, a positive result for anti-HBe).

The response rate of HBeAg seroconversion for a particular analysis population will be determined by:

$$\frac{\text{The number of patients with Negative HBeAg and Positive HBeAb at each visit}}{\text{The number of patients in each group for that analysis population}} \times 100\%.$$

Patients without either HBeAg or anti-HBe at 24 weeks after the end of treatment/principal observation period will be counted as non-responders. Patients in Group B who switched to receive PEG-IFN after Week 48 and prior to 24 weeks post-observation period will also be counted as non-responders.

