4.4.1.2 Hypothesis Testing and Analysis Methods

The following hypotheses will be tested using the Cochran-Mantel-Haenszel (CMH) test³ stratified by genotype (A vs. non-A) and ALT (< 5xULN and ≥ 5xULN) at screening:

H₀: odds ratio of {probability to achieve HBeAg seroconversion in group A} versus {probability to achieve HBeAg seroconversion in group B} = 1

against the alternative

H_a: odds ratio of {probability to achieve HBeAg seroconversion in group A} versus {probability to achieve HBeAg seroconversion in group B} ≠ 1.

The Cochran-Mantel-Haenszel estimates of the common odds ratio, adjusted by stratification factors (genotype (A vs. non-A) and ALT (< 5xULN and ≥ 5xULN)), will be reported, accompanied by the associated 95% confidence intervals. Breslow-Day test will be used to assess the homogeneity of the odds ratios across the strata. The CMH test stratified by genotype (A vs. non-A) and ALT (< 5xULN and ≥ 5xULN) at screening will also be performed based on the PP population.

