4.4.1.3 Sensitivity Analysis for Primary Endpoints

In addition to the stratified statistical tests, unstratified tests such as Pearson chi-square test and Fisher's exact test will be performed.

In the primary efficacy analysis, patients with missing values of primary endpoint will be considered as non-responders. In order to evaluate the robustness, sensitivity analysis will be carried out using CMH test, where missing values will be imputed with the approach of last observation carried forward (LOCF).

³ which is a superiority test.

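### The per-protocol set drops Group A children who stop before 39 doses but keeps Group B children who leave early as non-responders: a modest tilt toward PEG-IFN in a supportive analysis

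*SAP*

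**What the plan says.** SAP 4.1.2 lists seven reasons for exclusion from the PP set. Only the first depends on how long a child continued, and it is confined to Group A: a child is removed who "received less than 39 doses of PEG-IFN or took" 80% or less of the planned duration, which the SAP glosses as under 39 weeks. The other six apply to both groups. They cover HBeAg status, ALT and blood counts at entry, and use of other anti-HBV drugs. None asks for a minimum time under observation or an available endpoint in Group B.

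SAP 4.4.1.1 divides responders by "The number of patients in each group for that analysis population", so the denominator rule holds for PP as well as ITT. SAP 4.4.1.3 confirms that in the primary analysis "patients with missing values of primary endpoint will be considered as non-responders". SAP 4.4.1.2 adds that the stratified CMH test "at screening will also be performed based on the PP population". No separate missing-data rule is given for PP.

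SAP 4.4.1.1 also scores as non-responders those Group B children who switch to PEG-IFN between Week 48 and follow-up Week 24. Criterion 4 looks at Group B drug use only up to the switch, so it leaves these children in the PP set.

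**The concern.** Take a child who leaves the study at Week 10. In Group A the child has too few doses and drops out of both numerator and denominator. In Group B the child stays in the denominator as a failure. Early departure is therefore neutral in one arm and penalised in the other.

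PP is the only alternative population that the SAP applies to the primary endpoint. If its odds ratio exceeds the ITT odds ratio partly because of how the set was built, a reader may give it more weight than it deserves. The trial is open-label with different visit schedules by arm, so there is no reason to expect departures to be alike.

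**Working it through.** **Inputs.** Response rates of 32% (Group A) and 10% (Group B), two-sided 0.05, at least 80% power, N = 145: SAP 2.3. Allocation 2:1: SAP 3.1, giving about 97 and 48 children. The PP rule, denominator and missing-data rule are as set out above. Neither document gives a loss rate by arm. Assumption: a share d of each arm leaves before Week 39 with the Week 24 follow-up result missing, with d from 5% to 20%.

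**The plan's own figure.** The SAP states that "a total sample size of 145 patients provides at least 80% power at the 0.05 level of significance with a two-sided" chi-square test. The standard two-proportion formula at 2:1 gives 42 in Group B and 126 in total without continuity correction, and 48 and 144 with it. Power at 145 is 86.6%. The stated size is reproduced.

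**Effect of the one-sided rule.** Let pA = 0.32 and pB = 0.10 among those who stay.

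- ITT: pA(1 − d) against pB(1 − d)
- PP as written: pA against pB(1 − d)
- PP with the same rule in both arms: pA against pB
- Odds ratio: [a/(1 − a)] / [b/(1 − b)]

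| d | ITT | OR | PP as written | OR | PP, same rule | OR |
|---|---|---|---|---|---|---|
| 5% | 30.4% vs 9.5% | 4.16 | 32.0% vs 9.5% | 4.48 | 32.0% vs 10.0% | 4.24 |
| 10% | 28.8% vs 9.0% | 4.09 | 32.0% vs 9.0% | 4.76 | 32.0% vs 10.0% | 4.24 |
| 20% | 25.6% vs 8.0% | 3.96 | 32.0% vs 8.0% | 5.41 | 32.0% vs 10.0% | 4.24 |

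The PP difference is 22.5, 23.0 and 24.0 points, against 22.0 under the same rule: an excess of d × pB, or 0.5, 1.0 and 2.0 points. The odds ratio is raised by 6%, 12% and 28% (4.48, 4.76 and 5.41 divided by 4.24). At 10% loss the odds ratio rises by 0.67 from ITT to PP, of which 4.76 − 4.24 = 0.52 comes from the one-sided rule.

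**Direction.** Let r be the response rate of Group A early stoppers, and suppose Group B leavers would have responded at pB. With every outcome known, the difference would be pA(1 − d) + rd − pB. PP as written gives pA − pB(1 − d). The gap is d(pA − r) + d·pB. Both terms favour PEG-IFN when r is at most pA. The gap reverses only when r exceeds pA + pB = 42%. A matching Group B rule removes the second term only; the first is the ordinary selection effect of excluding early stoppers.

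**When there is no effect.** With both true rates at 10%, PP as written gives an odds ratio of 1.06, 1.12 and 1.28 at d = 5%, 10% and 20%. By exact enumeration of the unstratified chi-square test, the chance of a false result favouring PEG-IFN is 2.6%, 2.8% and 4.3%, against 1.9%, 1.9% and 1.8% under the same rule in both arms.

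**The case against.** The strongest reply is that criterion 1 is an exposure rule and not a dropout rule, and Group B has no doses to miss. Children who stop treatment are meant to return for follow-up (Protocol synopsis, 4.6.1 and 5.3). A Group A child with fewer than 39 doses may therefore have an observed result, and may even be an ITT responder whose removal lowers the PP rate. This stands. A reader might infer that every early stopper is a non-responder, and the documents do not support that. They do support the weaker condition used here: Protocol 6.2 expects prolonged low drug levels to reduce the chance of seroconversion. The criterion is also partly a duration rule, and Group B has a defined 48-week period to which a duration rule can apply.

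Second, the size. A reader might take the 28% inflation of the odds ratio as the expected effect, but it needs 20% of each arm lost before Week 39 with every endpoint missing. The footnote to SAP 2.3 requires at least 130 evaluable patients; against 145 that allows (145 − 130)/145 = 10.3% loss, up to follow-up Week 24. Evaluable is not defined, so this is only indicative. At 5% to 10% loss the shift is 48 × 0.10 × d = 0.24 to 0.48 of one expected Group B responder. The false-positive chance there is 2.6% to 2.8%, close to the nominal 2.5%.

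Third, ITT is primary, PP carries no success criterion, and SAP 4.4.1.3 names LOCF as the analysis for robustness. That stands too.

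**Conclusion.** The asymmetry is in the text and should be corrected, but it is modest and confined to a supportive analysis. On the planned rates and 5% to 10% equal loss with missing endpoints, the PP odds ratio is 4.48 to 4.76 instead of 4.24. The direction rests on Group A early stoppers responding no more often than completers; the loss rates are assumed. Only departures before 39 doses or weeks are treated differently: a Group A child lost later stays in PP as a non-responder, as in Group B.

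A reader might infer that the trial's main conclusion is biased toward PEG-IFN. The documents do not support that: the PP exclusions play no part in the primary ITT analysis, which scores missing results as non-response in both groups.

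**What to change.** Add to SAP 4.1.2 an exclusion parallel to criterion 1 for Group B children whose withdrawal date falls before 39 weeks of the principal observation period. Group B visits are at Weeks 12, 24, 36 and 48, so the rule has to rest on the withdrawal date, and the SAP should say which date is used for a child lost to follow-up.

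In the same edit, state how Group B children who switch before follow-up Week 24 are handled in PP. They cannot switch before Week 48, so the 39-week rule does not reach them. The SAP also assigns PP patients by treatment actually received, which leaves their place unclear.

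No added reporting is needed: SAP 4.2 already summarises exclusion reasons by group and lists withdrawals in both.

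The cost is a few lines of text and one reprogrammed population flag, settled before database lock as SAP 4.1 already requires for populations. A few Group B children leave the PP set (at 10% loss, about 43 remain of 48), and the PP odds ratio becomes slightly less favourable.

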4.1.3 Safety Population

For Group A, the Safety population included all patients who received at least one dose of study medication and had at least one post-baseline safety assessment; for Group B, the safety population included all patients who had at least one post-baseline safety assessment. Patients will be assigned to treatment groups as treated.

4.1.4 Pharmacokinetic (PK) Population

The pharmacokinetic evaluable population consists of all patients who are consented to PK sub-study and received PEG-IFN treatment, who have adequate PK collection over the first 24 weeks.

4.2 ANALYSIS OF STUDY CONDUCT

Reasons for exclusion from study populations will be summarized by groups. Patients excluded from study populations will be listed.

All major protocol violations will be listed and summarized by group.

Number and percentage of patients completed 12, 24, 36 and 48 weeks of treatment/principal observation period, and 12, 24 weeks of follow-up will be summarized for Group A and Group B.

The number of patients randomized to Group A who withdraw from treatment period, and the number of patients randomized to Group A and Group B who withdraw from study, will be separately summarized and presented; further the reasons for withdrawal will be included. Listing of withdrawal from study medication and withdrawal from study for all patients in Group A and Group B will be produced.

Time windows will be defined in DAP Module 2.

4.3 BASELINE CHARACTERISTICS

4.3.1 Demographics and Baseline Characteristics

Summary statistics will be presented for ITT population for the following demographics, including categorical variables:

Sex, Age group (<5, 5 ~ 12, ≥12), Race, Ethnicity, Body surface area group, Country and continuous variables:

age, weight at baseline, height at baseline, Body Mass Index (BMI), body surface area, weight for age percentile, height for age percentile, weight for age z-score, height for age z-score.

Summary statistics will be presented by ITT population for the baseline characteristics, including categorical factors:

- ALT at Baseline (<1xULN, ≥1xULN ~ <2xULN, ≥2xULN ~ <5xULN, ≥5xULN ~ <10xULN, ≥10xULN)
- HBV genotype
- Family history of HBV
- Mode of HBV acquisition
- Histological diagnosis for fibrosis
- Scale or method used for fibrosis score
- Fibrosis score

and continuous factors:

- HBV-DNA at Baseline
- HBeAg at Baseline
- HBsAg at Baseline
- ALT at Baseline.

4.3.2 Previous and Concomitant Diseases

All previous diseases and concomitant diseases will be summarized for ITT population.

4.3.3 Previous and Concomitant Medications

All previous medications and concomitant medications will be summarized for ITT population.

4.4 EFFICACY ANALYSIS

Analysis of all efficacy endpoints will be based primarily on the ITT population. In addition, the PP population will be used for the primary endpoint.

Unless otherwise stated, all statistical tests will be two-sided and performed at the 5% of significance level.

4.4.1 Primary Efficacy Endpoint

4.4.1.1 Definition of Primary Efficacy Endpoint

The primary efficacy endpoint is HBeAg seroconversion at 24 weeks after the end of treatment/ principal observation period for Group A and Group B. HBeAg seroconversion

is defined as absence of HBeAg (that is, a negative result for HBeAg) and presence of anti-HBe (that is, a positive result for anti-HBe).

The response rate of HBeAg seroconversion for a particular analysis population will be determined by:

$$\frac{\text{The number of patients with Negative HBeAg and Positive HBeAb at each visit}}{\text{The number of patients in each group for that analysis population}} \times 100\%.$$

Patients without either HBeAg or anti-HBe at 24 weeks after the end of treatment/principal observation period will be counted as non-responders. Patients in Group B who switched to receive PEG-IFN after Week 48 and prior to 24 weeks post-observation period will also be counted as non-responders.

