and ALT > ULN but $\leq 10 \times$ the ULN (using the reference range of the testing laboratory). Liver biopsy needs to have been performed within 2 years prior to baseline to confirm or exclude the presence of advanced fibrosis or cirrhosis (see Appendix 1). For subjects with advanced fibrosis, a liver biopsy needs to have been performed within 9 months prior to baseline to ensure that the subject has not progressed to cirrhosis. Subjects co-infected with HCV, hepatitis D virus (HDV), human immunodeficiency virus (HIV) or who have received therapy for hepatitis B in the prior 6 months or who have de-compensated liver disease will be excluded.

SECTION 4.2: INCLUSION CRITERIA

A subject may be included if the answer to all of the following statements is “yes”:

- Male or female subjects aged 3 to < 18 years old at baseline
- Positive HBsAg for more than 6 months
- Positive HBeAg and detectable HBV-DNA at screening (subjects must have > 10,000 copies/mL [$> 2,000$ IU/mL] as measured by PCR)
- ~~Negative anti-HBs and anti-HBe at screening. (Exception: subjects with positive antibodies based on central laboratory result but negative antibodies based on local laboratory result and who meet the other CHB inclusion criteria of positive HBsAg, positive HBeAg, detectable HBV-DNA, and elevated ALT may be included.)~~
- A liver biopsy performed within 2 years prior to baseline to confirm the presence of advanced fibrosis or exclude cirrhosis (see Appendix 1). For subjects with advanced fibrosis, a liver biopsy needs to be performed within 9 months prior to baseline
- Compensated liver disease (Child-Pugh Class A clinical classification; see Appendix 2)
- Elevated serum ALT > ULN but $\leq 10 \times$ the ULN as determined by two abnormal values taken ≥ 14 days apart during the 6 months before the first dose of study drug with at least one of the determinations obtained ≤ 35 days prior to the first dose. Reference range of the testing laboratory should be used
- Signed informed consent from parent/legal guardian and willingness of parent/legal guardian to abide by the requirements of the study, and signed assent from child if appropriate. *Patients <18 years of age at baseline who are legally adults according to national legislation must consent in their own right.*

SECTION 4.3: EXCLUSION CRITERIA

A subject will be excluded if the answer to any of the following statements is “yes”:

- Subjects with cirrhosis (see Appendix 1)

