4.2 INCLUSION CRITERIA

A subject may be included if the answer to all of the following statements is “yes”:

- Male or female subjects aged 3 to < 18 years old at baseline

- Positive HBsAg for more than 6 months
- Positive HBeAg and detectable HBV-DNA at screening (subjects must have > 10,000 copies/mL [$> 2,000$ IU/mL] as measured by PCR)
- A liver biopsy performed within 2 years prior to baseline to confirm the presence of advanced fibrosis or exclude cirrhosis (see [Appendix 1](#)). For subjects with advanced fibrosis, a liver biopsy needs to be performed within 9 months prior to baseline
- Compensated liver disease (Child-Pugh Class A clinical classification; see [Appendix 2](#))
- Elevated serum ALT > ULN but $\leq 10 \times$ the ULN as determined by two abnormal values taken ≥ 14 days apart during the 6 months before the first dose of study drug with at least one of the determinations obtained ≤ 35 days prior to the first dose. Reference range of the testing laboratory should be used
- Signed informed consent from *parent/legal guardian* and willingness of *parent/legal guardian* to abide by the requirements of the study, and signed assent from child if appropriate. *Patients <18 years of age at baseline who are legally adults according to national legislation must consent in their own right.*

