^a Parameter does not need to be repeated at re-screening if performed within 6 months prior to baseline, unless dictated by a change in the subject's medical condition or the parameter accounted for the original screen failure.

^b To be performed by local laboratory.

^c To be performed by a local laboratory in countries activated prior to April 2013, and by a central laboratory in countries activated after April 2013.

^d To be performed by central laboratory.

^e Estimated creatinine clearance will be calculated internally at baseline/switch baseline.

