8.2 STATISTICAL AND ANALYTICAL METHODS

8.2.1 Statistical Model

8.2.1.1 Primary Variables

The primary efficacy parameter is HBeAg seroconversion (defined as absence of HBeAg and presence of HBeAb) determined 24 weeks after the end of treatment/principal

observation period. Subjects with missing values for this parameter will be considered non-responders.

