8.2.1.2 Secondary Variables

All secondary variables will be determined at 24 weeks after the end of treatment/principal observation period and at 1, 2, 3, 4, and 5 years after the end of treatment/principal observation period.

- Loss of HBeAg (defined as absence of HBeAg)
- HBsAg seroconversion (defined as loss of HBsAg and presence of anti-HBs)
- Loss of HBsAg (defined as absence of HBsAg)
- Quantitative serum ALT
- Proportion of normal serum ALT (defined as ALT measure \leq ULN)
- Quantitative HBV-DNA
- Suppression of HBV-DNA $< 100,000$ copies/mL ($< 20,000$ IU/mL), $< 10,000$ copies/mL ($< 2,000$ IU/mL), undetectable, and change from baseline
- Combined endpoints: HBeAg seroconversion and HBV-DNA $< 100,000$ copies/mL ($< 20,000$ IU/mL)
- Combined endpoints: HBeAg seroconversion and HBV-DNA $< 10,000$ copies/mL ($< 2,000$ IU/mL)
- HBeAg seroconversion (defined as absence of HBeAg and presence of HBeAb)

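### The primary endpoint reads only final HBeAg/anti-HBe status and no rule uses the day 1 sample, so a child already HBeAg negative on day 1 counts as a seroconversion

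*SAP*

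**What the plan says.** **Endpoint.** SAP 4.4.1.1 states that seroconversion "is defined as absence of HBeAg (that is, a negative result for HBeAg) and presence of anti-HBe", and the numerator of the response rate is "The number of patients with Negative HBeAg and Positive HBeAb at each visit". Protocol 8.2.1.1 gives the same status definition: "HBeAg seroconversion (defined as absence of HBeAg and presence of HBeAb". The word loss adds no starting condition, because Protocol 8.2.1.2 reads "Loss of HBeAg (defined as absence of HBeAg".

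**Entry.** Protocol 4.2 asks for "Positive HBeAg and detectable HBV-DNA at screening". Protocol 4.1 to 4.3 set no condition on anti-HBe and none on the day 1 HBeAg result.

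**Age of the screening result.** Protocol 5.1 allows 35 days before randomisation, with a 7-day extension in exceptional cases. For HBV serology and virology, footnote a of Table 5 adds: "Parameter does not need to be repeated at re-screening if performed within 6 months prior to baseline". Reuse is barred if the child's medical condition changed or if that test caused the first screen failure.

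**Day 1 sample.** Protocol Tables 2 and 3 schedule HBeAg and anti-HBe at baseline in both arms, frozen for the central laboratory. No text makes randomisation or response depend on the result.

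**Analysis sets and checks.** The ITT set (SAP 4.1.1) has no serology condition. Per-protocol criterion 2 (SAP 4.1.2) removes only those "HBeAg negative at screening". The sensitivity analyses in SAP 4.4.1.3 are unstratified tests and LOCF. SAP 4.3.1 summarises HBeAg at baseline as a continuous factor, and SAP 4.4.3 splits it at the median. Neither section uses baseline anti-HBe.

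**The concern.** The primary objective is to compare seroconversion between treated and untreated children. Seroconversion is a change, but the plan counts a state. The two agree only if every child starts HBeAg positive on day 1, and the plan checks that at screening, not on day 1.

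Two kinds of child need to be kept apart:

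1. **HBeAg negative on day 1.** If this child is HBeAg negative and anti-HBe positive at follow-up Week 24, the rule counts a response although HBeAg did not change on study. The same holds for the secondary endpoint of HBeAg loss. This is a misclassification.
2. **HBeAg positive and anti-HBe positive on day 1.** This child must still lose HBeAg to respond. The anti-HBe half of the endpoint is met at the start, so the endpoint reduces to HBeAg loss. That changes what is measured for this child but is not a misclassification. It is a matter for sensitivity analysis.

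At stake are the meaning of a response and, to a small extent, the control rate. With about 48 controls and a planned rate of 10%, fewer than five control responders are expected (48 × 0.10 = 4.8).

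**Working it through.** **Inputs.** Rates of 32% (A) and 10% (B), total 145, two-sided 0.05 (SAP 2.3). Allocation 2:1 (SAP 2), so about 97 and 48. Spontaneous seroconversion in the immunoactive phase of 8–12% (Protocol 1.1.1), given without a time unit; *per year is my assumption*. The share f already converted on day 1 is not in the documents.

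**Step 1: reproduce the plan's figure.** The two-proportion formula with continuity correction, 2:1, gives 48 + 96 = 144, against 145 stated. Without the correction it gives 42 + 84 = 126. The sample size is not in error.

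**Step 2: baseline power at 97:48.** Power = Φ[(d − 1.96·SE0)/SE1].
- d = 0.32 − 0.10 = 0.22
- pooled p = (97 × 0.32 + 48 × 0.10)/145 = 0.247
- SE0 = √[0.247 × 0.753 × (1/97 + 1/48)] = 0.0761
- SE1 = √[0.32 × 0.68/97 + 0.10 × 0.90/48] = 0.0642
- (0.22 − 1.96 × 0.0761)/0.0642 = 1.10, so power = 0.865

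**Step 3: how many convert before day 1.** Share = 1 − (1 − r)^(w/52).

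| Age of result | r = 8% | r = 12% | Applies to |
|---|---|---|---|
| 5 weeks | 0.8% | 1.2% | all children, at the limit of the window |
| 6 weeks | 1.0% | 1.5% | approved extension only |
| 26 weeks | 4.1% | 6.2% | re-screened children with a reused result 6 months old |

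At 5 weeks this is 145 × 0.008 = 1.2 to 145 × 0.012 = 1.7 children. The number re-screened is not given, so the last row cannot be turned into a count.

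**Step 4: effect on the comparison.** Assume every such child is still converted at the endpoint and the share f is the same in both arms. Each rate becomes f + (1 − f)p.

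| f | A | B | Odds ratio | Power at 97:48 |
|---|---|---|---|---|
| 0 | 32.0% | 10.0% | 4.24 | 0.865 |
| 0.8% | 32.5% | 10.7% | 4.02 | 0.851 |
| 1.2% | 32.8% | 11.1% | 3.92 | 0.843 |

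At f = 1%, such children make up 0.01/0.109 = 9% of Group B responders.

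**Step 5: chance imbalance.** One such child moves the Group B rate by 1/48 = 2.1 points or the Group A rate by 1/97 = 1.0 point. If there were three, the chance that all fall in A is (97 × 96 × 95)/(145 × 144 × 143) = 30%, and that all fall in B is (48 × 47 × 46)/(145 × 144 × 143) = 3.5%.

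**Step 6: under the proposed rule.** With baseline-negative children counted as non-responders, each rate becomes (1 − f)p. At f = 1% this is 31.7% against 9.9%, odds ratio 4.22, compared with 3.97 under the current rule. The difference is 21.8 points either way.

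**The case against.** The case against giving this weight is strong on several points.

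- **HBeAg positivity is still an entry condition.** A reader might infer that the protocol dropped it. It did not. The summary of changes shows only that the condition "Negative anti-HBs and anti-HBe at screening" was struck out. That is amendment history and no error, and this point does not ask for it back. The 6-month reuse is narrow: one re-screening, with Medical Monitor approval, and the two bars noted above.
- **The anti-HBe-positive child is handled as the protocol defines the endpoint**, which asks for presence of anti-HBe and not its appearance. This stands.
- **Nothing favours PEG-IFN in expectation.** The status arises before treatment, so randomisation balances it. The effect is dilution of the odds ratio, and the test keeps its error rate. This stands; chance imbalance can go either way.
- **A large power loss is not shown.** A reader might infer that admitting anti-HBe-positive children takes power well below 80%. The documents give neither their share nor their untreated rate of HBeAg loss. Suppose 5–15% and 30–50% (both assumptions). Power at 97:48 is then 0.84–0.88 if the planned odds ratio of 4.24 holds in that subgroup, and 0.80–0.85 if the planned 22-point difference holds. A much lower figure needs almost no treatment effect in these children, which nothing in the documents suggests.
- **The plan is not blind to baseline HBeAg.** The quantitative summary and the median split would place a child who had lost HBeAg in the low group. What they do not give is a count of HBeAg-negative children or any anti-HBe status.

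The objection does not remove the gap itself: no rule stops a child already HBeAg negative on day 1 from counting as a response.

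**Conclusion.** The point holds in a limited form. The response rule misclassifies a child who is HBeAg negative on day 1, and no entry rule, analysis set or sensitivity analysis corrects for this. The expected number is about 1 to 2 of 145. Power falls from 0.865 to about 0.85–0.84, still above the 80% in the plan. These figures rest on reading 8–12% as an annual rate, on screening results at the 5-week limit, and on all such children remaining converted. Reused re-screening results could add to the number by an amount that the documents do not allow one to estimate.

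The case for acting is not power. It is that the rule should measure what the objective names, that fewer than five control responders are planned, and that in an open-label trial the handling of such children should be settled before the data are examined.

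**What to change.** 1. **SAP 4.4.1.1 and the HBeAg-loss endpoint in 4.4.2:** count as responders only children HBeAg positive on the day 1 central sample. Keep baseline-negative children in the ITT denominator as non-responders, in both arms alike. State what applies if the day 1 result is missing.
2. **SAP 4.1.2:** extend per-protocol criterion 2 to HBeAg negative at screening or baseline.
3. **SAP 4.4.1.3:** add the stratified CMH analysis restricted to children HBeAg positive and anti-HBe negative at baseline.
4. **SAP 4.3.1:** tabulate qualitative baseline HBeAg and anti-HBe status by arm.

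The changes should be made before database lock. They need no new visit or sample: both arms already have the day 1 draw, and Protocol 5.3 places Group A's baseline assessments before the first dose. The cost is one clause, one amended criterion, one table row and one sensitivity analysis with slightly fewer children. The reported response rate may be slightly lower in both arms.
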